- 286 4) Assess if Fiasp® becomes less effective over the life an infusion set (are sets
287 changed more frequently)
- 288 5) Assess how the 670G performs when Fiasp® is used:
 - 289 a. Do insulin-to-carbohydrate ratios need to be modified
 - 290 b. Does duration of insulin action need to be modified
 - 291 c. Is more or less basal insulin delivered
 - 292 d. Does the total daily dose change
 - 293 e. Does the performance of the 670G change overnight (MN to 6AM)
294 and during the day (6AM to MN) in terms of time in range, mean
295 glucose and % of readings <70 mg/dL.

296

297 will include both males and females and an enrollment goal will be to achieve an

298 approximately equal sex distribution. Their total daily insulin dose should be at least
299 0.3 units/kg/day and they should be eating at least 60 grams of carbohydrate each
300 day.

301

302 **General Considerations**

303 The study is being conducted in compliance with the policies described in the study
304 policies document, with the ethical principles that have their origin in the Declaration
305 of Helsinki, with the protocol described herein, and with the standards of Good
306 Clinical Practice.

307

308 **CHAPTER 2: SUBJECT ENROLLMENT AND STUDY INITIATION**

309

310 **Study Enrollment and Duration**

311 Part 1: Randomized cross-over, blinded study with assessment of meal
312 pharmacodynamics: up to 20 subjects will be studied and the studies for each
313 subject will last 6 weeks.

314 Part 2: Long term use of Fiasp®. We will recruit up to 20 subjects who are using
315 Fiasp® insulin, they are not excluded if they were in Part 1, in fact subjects in part 1
316 will be encouraged to continue into part 2 of the study. Duration is up to 6 weeks, or
317 until subject decides to stop using Fiasp®.

318

319 **Eligibility and Exclusion Criteria**

320

321 **Eligibility Criteria**

322 To be eligible for the study, a subject must meet the following criteria:

- 323 1. Clinical diagnosis of type 1 diabetes and using 670G pump for at least 1
324 month, and willing to have the 670G pump downloaded into a Carelink
325 Clinical research database.
- 326 2. The diagnosis of type 1 diabetes is based on the investigator's judgment; C-
327 peptide level and antibody determinations are not needed.
- 328 3. Age ≥18 years
- 329 4. Using Novolog or Fiasp® insulin at time of enrollment
- 330 5. Willing to use Fiasp® insulin
- 331 6. Total daily insulin dose is at least 0.3 units/kg/day

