529 670G pump to a research Carelink account every 2 weeks. Their data will be
530 reviewed within 3 days by the clinicians managing the study at each research
531 clinical site. An email, text or phone call will be made to the subject after reviewing
532 their pump/sensor data. Recommendations for dosage changes will be recorded on
533 a case report form or directly into RedCap. The study investigators will meet every
534 2 to 4 weeks during the study to review clinical issues and insights that have been
535 observed.

536

537 To assess the long term effect of using Fiasp® on infusion sites and insulin action,
538 they will be asked to use Fiasp® as long as they see benefit in using it after the
539 initial meal boluses testing is completed. Each time they change their infusion set,
540 we will ask them to examine the site for any bleeding, redness or induration, and
541 measure these changes and take a picture if there are any findings. (See
542 Documentation of infusion site reactions). We will have them download to a
543 CareLink research data base every two weeks to look at their total daily insulin
544 requirements, glucose values, and basal insulin requirements with extended use of
545 Fiasp®. They will have an email sent to them every 2 weeks by RedCap to assess
546 for issues they have observed while using Fiasp®.

547

548 *Documentation of infusion site reactions:* At home subjects will exam their infusion
549 set site when they are changing an infusion set and assess for bleeding, signs of a
550 local tissue reaction or infection. They will record redness, induration, and bruising
551 in mm, and call one of the investigators if there is more than 10 mm of erythema or
552 induration. They will be given a ruler for making these measurements. If there is
553 more than 3 mm of induration or redness they will be asked to take a picture and
554 enter these measurements and send a text to the study coordinator or submit the
555 information directly into RedCap.

556

557 They will be instructed to replace the infusion set if:

- 558 1. Their ketone level is greater than 0.6 mmol/L,
- 559 2. There is evidence of infection at the infusion site
- 560 3. Their blood glucose (meter) does not decrease by at least 50 mg/dL within 1
561 hour of a correction bolus for unexplained hyperglycemia with a blood
562 glucose greater than 250 mg/dL.
- 563 4. There is a pump occlusion alarm.

564

565 **CHAPTER 4: ADVERSE EVENT REPORTING AND PROTOCOL MONITORING**

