687 used to secure the CGM sensor, or to secure the insulin infusion sets for the
688 Continuous Subcutaneous Insulin Infusion (CSII). If these reactions occur, different
689 adhesives or “under-taping” (such as with IV 3000, Tegaderm, etc.) will be tried,
690 sites will be rotated frequently, and a mild topical steroid cream or other medication
691 may be required.

692

693 Whenever the skin is broken there is the possibility of an infection. The CGM
694 sensor and insulin infusion set sites are inserted under the skin. It is possible that
695 any part that is inserted under the skin may cause an infection. These occur very
696 infrequently, but, if an infection was to occur, oral and/or topical antibiotics can be
697 used. The risk of skin problems could be greater if a sensor or infusion set is used
698 for extended periods of time. Therefore participants will be carefully instructed
699 about daily inspection of their sensor and infusion set sites.

700

701 Data downloaded from the CGM sensor, insulin pump, and the home glucose and
702 ketone meters will be collected for the study as measures of diabetes self-
703 management behaviors. Some people may be uncomfortable with the researchers'
704 having such detailed information about their daily diabetes habits.

705

706 **CHAPTER 5: MISCELLANEOUS CONSIDERATIONS**

707

708 **Potential Benefits**

709 Fiasp® may provide a more rapid onset of insulin action and improved post-prandial
710 glycemic control.

711

712 **Subject Compensation**

713 For Part 1, participants will be compensated \$50 for each visit, \$15 for completing
714 weekly uploads to Carelink for a maximum payment of \$245. For part 2, subject will
715 receive \$50 for each visit, and \$20 for uploading to Carelink and contact with the
716 investigators every two weeks they are in the extension phase. Maximum payment
717 of \$160. Compensation of partial participation will be prorated.

718

719 **Subject Withdrawal**

720 Participation in the study is voluntary, and a subject may withdraw at any time. The
721 investigator may withdraw a subject who is not complying with the protocol. For
722 subjects who withdraw, their data will be used up until the time of withdrawal.

723

724 **Subject Discontinuation Criteria**

725 Subjects who become pregnant will be discontinued from the study. The
726 investigator may withdraw a subject who is not complying with the protocol.

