727 Withdrawal of a subject will be considered for the following reasons: 1) Failure to
728 monitor their sensor and infusion sites on a daily basis; 2) developing >1.0 mmol/L
729 ketones on 2 or more occasions and failing to change their infusion set or a single
730 episode of diabetic ketoacidosis due to an infusion site failure. For subjects who
731 withdraw or who are withdrawn, their data will be used for analysis purposes up until
732 the time of withdrawal.

733

734 **Confidentiality**

735 For security and confidentiality purposes, subjects will be assigned an identifier that
736 will be used instead of their name. De-identified subject information may also be
737 provided to Medtronic Diabetes.

738

739 **Level of Risk**

740 This research proposal in children is consistent with United States Department of
741 Health and Human Services, Protection of Human Subjects, Subpart D, Section
742 46.404 (Research not involving more than minimal risk).

743

744 **Planned Duration of the Entire Study**

745 Planned duration of the entire study will be 6 months.

747 **CHAPTER 6: STATISTICAL CONSIDERATIONS**

748

749 This is a pilot study to determine if there are any clinical issues with using Fiasp® in
750 the 670G hybrid closed-loop system. These studies are not statistically powered.

751

752 In the blinded cross-over studies (Part I) we will use data obtained during the
753 second week of each arm to compare the following measurements using a mixed-
754 effects model accounting for crossover study design of the study with the sequence
755 of treatment nested within the patient:

756

a) time in range (70-180 mg/dl)

757

b) percent time <70 mg/dl,

758

c) mean glucose,

759

d) glucose CV,

760

e) total daily insulin dose,

761

f) total daily basal insulin,

762

g) insulin delivery from MN to 6AM, and 6AM to MN

763

764 We will test to see if there is any difference in pharmacodynamics when using
765 Fiasp® in the home environment when they are eating their usual breakfast.

766

767 Insulin pharmacodynamics following the standard breakfast will be assessed by
768 measuring the peak glucose concentration (C_{max}), time to C_{max} (t_{max}), and estimated
769 average glucose excursions were assessed using sensor glucose values at a time
770 interval of 0 to 180 minutes after breakfast bolus. If a bolus was given between
771 120-180 minutes following the breakfast bolus, CGM values were only used up to

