772 the time of the bolus. The glucose at the time of the breakfast bolus (Time 0) will be
773 set to 0 mg/dL for each meal, and the remaining CGM values were adjusted
774 proportionally to allow analysis of postprandial glucodynamic parameters. We will
775 utilize a mixed-effects model accounting for crossover study design of the study with
776 the sequence of treatment nested within the patient. Breakfast meals are excluded
777 from postprandial analysis if: 1) the rate of change was greater than 0.3mg/dL/min
778 in the 1 hour prior to breakfast, 2) subjects gave a subsequent bolus prior to 120
779 minutes following the breakfast bolus, or 3) subjects deviated from their typical
780 breakfast. Dinner meals will be assessed when there has been no additional food
781 intake after dinner. The duration of insulin delivery to cover the meal will be
782 determined by the time it takes the post prandial glucose to reach 160 mg/dL
783 beyond 1 hour of eating. The peak glucose will also be recorded.

783

784 During the 6 week optimization study (Part II) we will use data obtained during the
785 first two weeks of the study (before data was reviewed and changes made by the
786 investigators) to data obtained during the last two weeks of the 3 month optimization
787 period. We will compare the following measurements using paired t-tests for data
788 with a normal distribution and a Mann-Whitney rank sum test for data that is not
789 normally distributed:

790

a) time in range (70-180 mg/dl)

791

b) percent time <70 mg/dl,

792

c) mean glucose,

- 793 d) glucose CV,
- 794 e) total daily insulin dose,
- 795 f) total daily basal insulin,
- 796 g) insulin delivery form MN to 6AM, and 6AM to MN
- 797 h) CHO:I ratios at breakfast, lunch and dinner
- 798 i) Active insulin time
- 799 j) Number of days between infusion set changes
- 800 k) Erythema (mm) and induration (mm) at infusion sites when they are changed
- 801 l) Average daily insulin, and mean glucose for each day of infusion set wear
- 802 m) Number of episodes of unexplained hyperglycemia in the first month vrs the
- 803 last month
- 804
- 805
- 806
- 807

808 **CHAPTER 7: REFERENCES**

809

- 810 1. Heise T, Hovellmann U, Nosek L, Sassenfeld B, Thomsen KMD, Haahr H.
811 Pharmacokinetic Properties of Fast-acting Insulin Aspart Administered in Different
812 Subcutaneous Injection Regions: Response to the commentary by Nuggehally R. Srinivas.
813 Clinical drug investigation 2017.

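### Part 2 can end early when a subject stops Fiasp, but Chapter 6 does not say how a subject without a last-two-week window enters the before-after comparison

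*Combined protocol and SAP*

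**What the plan says.** Length of Part 2. Chapter 2, Study Enrollment and Duration, says that Part 1 subjects "will be encouraged to continue into part 2 of the study. Duration is up to 6 weeks, or" "until subject decides to stop using Fiasp". Chapter 3, Part 2, adds that "they will be asked to use Fiasp® as long as they see benefit in using it after the" initial meal testing is done. Synopsis 1.4 also gives 6 weeks. The HbA1c paragraph of Chapter 2 speaks of a 3-month observational study.

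The comparison. Chapter 6 opens its Part II paragraph with a 6-week study. It takes as the before window the "first two weeks of the study (before data was reviewed and changes made by the" investigators, and ends the same sentence with "investigators) to data obtained during the last two weeks of the 3 month optimization" period. The tests follow: "period. We will compare the following measurements using paired t-tests for data" that are normal, and a Mann-Whitney rank sum test otherwise. Item (m), unexplained hyperglycemia, is compared between the first and last month instead. Item (l) is broken down by day of set wear.

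Early exit. Chapter 5, Subject Withdrawal, says that for "subjects who withdraw, their data will be used up until the time of withdrawal". Subject Discontinuation Criteria repeats this for subjects whom the investigator withdraws. Chapter 6 names no analysis set and no missing-data rule, and does not list stopping, its day or its reason as an outcome.

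**The concern.** Exit from Part 2 is tied to whether the subject perceives benefit, and the main comparison needs data from the end of the period. Using data up to withdrawal does not help, because it supplies no after value. A comparison limited to subjects who reach the end is therefore a selected one.

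Part 2 sets out to learn about local reactions, loss of effect over set life and 670G performance on Fiasp. Chapter 4 names local reactions and more frequent site changes as possible risks, and either is a plausible reason to stop. In a pilot meant to uncover clinical issues, how many subjects stop, when and why is itself a main finding, and no analysis of it is planned.

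**Working it through.** The plan gives no power, alpha or stopping figure for Part 2, so there is no figure to reproduce.

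**1. Which subjects have an after value?** Let d be the day of stopping.

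- Fixed 6-week (42-day) period: before window days 1–14, after window days 29–42. For d ≤ 28 there is no after value. For d = 29 to 41 there are d − 28 days.
- Fixed 3-month period: a subject held to the 6-week cap has no after value, whether or not Fiasp was stopped early.
- Subject's own last 14 days (not written, but compatible with using data up to withdrawal): for d between 14 and 28 the overlap with the before window is 28 − d days. At d = 28 it is 0, at d = 21 it is 7 of 14, and at d = 14 it is all 14, which forces a change of zero.

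**2. Effect on a paired comparison.** For n enrolled subjects, of whom s stop:

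completers' mean change − all-enrolled mean change = (s/n) × (mean change in continuers − mean change in stoppers).

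Illustration with assumed changes in time in range of +3 for continuers and −8 for stoppers, n = 20. The completers' result is always +3.0. The all-enrolled means are:

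- s = 2: (18 × 3 − 2 × 8)/20 = +1.9
- s = 4: (16 × 3 − 4 × 8)/20 = +0.8
- s = 6: (14 × 3 − 6 × 8)/20 = −0.3

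The formula gives zero when the two mean changes are equal, and the opposite sign if stoppers would have improved more.

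**3. Simulation with true mean change zero.** The SDs of time in range are borrowed from Table 1 (12.2 at run-in, 8.8 at 3 months). They come from a different study. The before-after correlation r is assumed to be 0.5 to 0.8.

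SD of change = √(12.2² + 8.8² − 2r × 12.2 × 8.8) = 10.9 at r = 0.5 and 7.4 at r = 0.8.

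There were 20,000 runs with n = 20 and a two-sided 5% paired t-test on those who remain. Each cell shows the bias in points over the two values of r, then the rate of false improvement (nominal 2.5%). The columns are the assumed correlation between stopping and the subject's own worsening.

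| Stoppers of 20 | 0 | 0.5 | 1 (upper bound) |
|---|---|---|---|
| 2 | 0; 2.5% | 0.7–1.0; 6% | 1.3–2.0; 15% |
| 4 | 0; 2.5% | 1.2–1.8; 10% | 2.5–3.6; 38% |
| 6 | 0; 2.5% | 1.8–2.6; 14% | 3.5–5.2; 62% |

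**4. Effect on the unpaired fallback.** A stopper can remain in the before group with nothing in the after group. Suppose nobody changes, 4 stoppers sit at 60% time in range and 16 continuers at 72% (assumed). The before mean is (4 × 60 + 16 × 72)/20 = 69.6 and the after mean is 72. The apparent gain of 2.4 points comes from composition alone.

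**The case against.** A reader might infer that subjects for whom Fiasp fails vanish from every before-after result, and that the results must then flatter Fiasp. The documents do not support this.

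- Not every result. Only normally distributed data get a paired test. The Mann-Whitney fallback needs no pair, and item (m) uses months. Late stoppers keep part of the after window, and on the own-last-two-weeks reading anyone stopping at week 4 or later keeps two separate windows.
- Not simply failures. Stopping is the subject's decision. Some with poor results may continue, and others may stop for unrelated reasons. Part 2 also has a 6-week cap.
- Direction not shown. Entrants already use Fiasp in usual care, so both windows are on Fiasp and the contrast is before versus after the clinicians' adjustments. A subject who does equally poorly in both windows has a change near zero.
- Problems before stopping are recorded. Sites are inspected at each set change, a questionnaire goes out every two weeks, and adverse events are elicited at visits. The studies are also declared unpowered.

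All of this limits the claim, and the direction can only be called probable. It does not remove the gap. The fallback replaces exclusion with a change in composition, and the own-last-two-weeks window is not what Chapter 6 states. Selection before entry does not undo selection after it. Recording problems is not the same as planning to report who stopped and why. Lack of power does not excuse a selected comparison.

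**Conclusion.** The point holds in limited form. Part 2 may end early on perceived lack of benefit, and Chapter 6 has no rule for subjects who then lack the after window. On a fixed 6-week window, those stopping by the end of week 4 are lost from any paired t-test and sit in the before group only under Mann-Whitney. If stopping tracks the subject's own change, the comparison is biased, probably towards a better result, because the stated condition for continuing is perceived benefit.

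The size cannot be known from the documents. At a correlation of 0.5 with 2 to 6 of 20 stopping, it is about 0.7 to 2.6 points of time in range, with false improvement in about 6% to 14% of trials. At zero correlation there is no bias. These figures rest on assumed stopping numbers and correlations and on borrowed SDs. The plan should be amended, but the point does not invalidate the pilot.

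**What to change.** In Chapter 6, Part II:

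1. Report, for all enrolled subjects, the number stopping Fiasp, the day and the reason.
2. For early stoppers, define the after window as the last 14 days on Fiasp that fall after day 14, using whatever days exist. This gives min(14, d − 14) days: 7 for a stop on day 21, and 14 from day 28 on. Report this comparison beside the completers' comparison, and label the latter as covering subjects still using Fiasp. List separately those who stop by day 14, who have no after value under any definition.
3. Use a paired test throughout, with the Wilcoxon signed-rank test replacing Mann-Whitney for non-normal data.
4. Collect the final pump upload and questionnaire at the time of stopping.
5. Reconcile the Part 2 duration statements, since they set the after window: 6 weeks (Synopsis 1.4, Chapter 2, opening of the Part II paragraph in Chapter 6), 3 months (HbA1c paragraph of Chapter 2, same sentence of Chapter 6), and use while benefit is seen (Chapter 3). Item (m) depends on this too: with 4-week months, the first and last month of a 6-week period share 4 + 4 − 6 = 2 weeks.

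The cost is wording and a short stopping form. The downside is that early stoppers' windows are shorter and noisier. No change to when a subject may stop is proposed.

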566
567 **Definition**

568 A reportable adverse event is any untoward medical occurrence that meets criteria
569 for a serious adverse event or any unexpected medical occurrence in a study
570 subject that is study or device-related. Skin irritation from sensor wear will be
571 recorded in specific sections of the case report forms. An adverse event form is
572 only completed if skin irritation is severe or antibiotics are required.

573
574 Hypoglycemic events are recorded as Adverse Events if the event required
575 assistance of another person due to altered consciousness to actively administer
576 carbohydrate, glucagon, or other resuscitative actions. This means that the subject
577 was impaired cognitively to the point that he/she was unable to treat him or herself,
578 was unable to verbalize his or her needs, was incoherent, disoriented, and/or
579 combative, or experienced seizure or coma. These episodes may be associated
580 with sufficient neuroglycopenia to induce seizure or coma. If plasma glucose
581 measurements are not available during such an event, neurological recovery
582 attributable to the restoration of plasma glucose to normal is considered sufficient
583 evidence that the event was induced by a low plasma glucose concentration.

584
585 Hyperglycemic events are recorded as Adverse Events if the event involved diabetic
586 ketoacidosis (DKA), as defined by the DCCT, and had all of the following:

- 587 1) Symptoms such as polyuria, polydipsia, nausea, or vomiting
588 2) Serum ketones greater than 1.6 mM, or large/moderate urine ketones
589 3) Either arterial blood pH <7.30 or venous pH <7.24 or serum bicarbonate <15
590 4) Treatment provided in a health care facility

591
592 **Recording of Adverse Events**

593 Throughout the course of the study, all efforts will be made to remain alert to
594 possible adverse events or untoward findings. The first concern will be the safety of
595 the subject, and appropriate medical intervention will be made.

596
597 The investigator will elicit reports of adverse events from the subject at each visit
598 and complete all adverse event forms online. Each adverse event form is reviewed
599 by the Coordinating Center to verify the coding and the reporting that is required.

600
601 The study investigator will assess the relationship of any adverse event to be
602 related or unrelated by determining if there is a reasonable possibility that the

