648 device event that is both serious and unexpected. Notification will be made within
649 10 days after becoming aware of the event.

650
651 [name] will inform the IRB of serious study-related adverse events and
652 abide by any other reporting requirements specific to their IRB.

653
654 **Potential Risks and Side Effects**

655 There may be a higher frequency of hypoglycemia immediately following a meal bolus.
656 There may be prolonged hyperglycemia following a high fat meal. There may be local tissue

657 reactions at the FIASP® infusion sites. Infusion sites may need to be changed more
658 frequently than usual when infusing FIASP®. As with any insulin, there is a risk for both
659 high and low blood glucose levels occurring if there is a mismatch between your insulin
660 needs and the insulin levels provided by the insulin. See hypoglycemia and hyperglycemia
661 risks below. It is very rare, but allergic reactions to insulin may occur.

662

663 **Risk of Hypoglycemia**

664 As with any person having insulin-dependent diabetes, there is always a risk of
665 having a low blood sugar (hypoglycemia). The frequency of nocturnal
666 hypoglycemia should be no more than it would be as part of daily living with
667 diabetes. Symptoms of hypoglycemia can include sweating, jitteriness, and not
668 feeling well. Just as at home, there is the possibility of loss of consciousness or
669 seizures (convulsions) and that for a few days you may not be as aware of
670 symptoms of low blood sugar. Even if severe low blood sugar does occur, it almost
671 always goes away quickly with treatment to raise the blood sugar.

672

673 **Risk of Hyperglycemia**

674 As with any person having insulin-dependent diabetes, there is always a risk of
675 having a high blood sugar (hyperglycemia). The frequency should be no more than
676 it would be as part of daily living with diabetes.

677

678 **Protection Against Risks and Treatment of Side Effects:**

679 Subjects will be given descriptions of possible side effects from wearing an infusion
680 set, and local side effects with insulin infusion sets or Guardian sensor insertion
681 sets. They will be told to contact the study staff if they see any signs of a skin
682 reaction. Based on the severity of local skin reaction, topical anti-inflammatory
683 medications can be used (such as topical steroids).

684

685 **Other Risks**

686 Some subjects may develop skin irritation or allergic reactions to the adhesives

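### The adverse-event definition conflicts with the recording text and leaves non-serious allergic reactions, ketosis and infusion-site reactions without an assured record in the blinded Fiasp–aspart comparison

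*Combined protocol and SAP*

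**What the plan says.** Chapter 4, Definition, begins "A reportable adverse event is any untoward medical occurrence that meets criteria" and continues "for a serious adverse event or any unexpected medical occurrence in a study". The line after that closes the definition with a relatedness condition and opens a skin rule: "subject that is study or device-related. Skin irritation from sensor wear will be" entered in dedicated case report form sections, with an adverse event form "only completed if skin irritation is severe or antibiotics are required".

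Two more rules follow. "Hypoglycemic events are recorded as Adverse Events if the event required" help from another person because of altered consciousness. Hyperglycemic events qualify if they involved diabetic "ketoacidosis (DKA), as defined by the DCCT, and had all of the following", after which come four conditions, the last being treatment in a health care facility.

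Chapter 4, Recording of Adverse Events, has the investigator elicit events at each visit, judge each one related or unrelated to the device or procedures, grade it mild, moderate or severe, and code it in MedDRA. Its example of a severe but non-serious event is itching.

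Chapter 4, Potential Risks and Side Effects, foresees hypoglycemia after meal boluses, prolonged hyperglycemia after fatty meals, and local tissue "reactions at the FIASP® infusion sites. Infusion sites may need to be changed more" often. It closes by pointing to the glucose "risks below. It is very rare, but allergic reactions to insulin may occur".

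Chapter 3 has subjects record site bleeding, redness, induration and bruising when an infusion set fails (the Visit 1 training text, which governs Part 1), and at every set change in Part 2. Chapter 6 lists items a–g for the Part 1 comparison, all of them CGM or insulin-delivery measures, followed by the breakfast and dinner glucose analyses.

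**The concern.** Under the definition, a non-serious event must be both unexpected and related. The protocol itself foresees the likely tolerability problems of Fiasp in a pump, so their ordinary forms fail the first test. The recording text describes a different system, in which events of every intensity are elicited and their relationship to the study is assessed afterwards. A site cannot tell which of the two decides whether a form is completed.

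This matters most in Part 1. Chapter 6 gives the purpose as finding out whether there are clinical issues with Fiasp in the 670G, and Part 1 is the only place where Fiasp is set against aspart under blinding. Part 2 requires Fiasp as usual care and so has no aspart comparator. If the narrow definition governs, a sparse Part 1 listing would reflect the definition at least as much as tolerability. The count would also depend on judgements of expectedness and relatedness made before anything is recorded.

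**Working it through.** The plan gives no figure to reproduce; this is a check of text against text. Each foreseen event is run through the definition (serious, or unexpected and related), then the added rules, then capture elsewhere.

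| Event, non-serious form | Definition | Added rule | Other capture in Part 1 | In Part 1 comparison |
|---|---|---|---|---|
| Hypoglycemia, unassisted | Not met | Not met | CGM time <70 mg/dL | Yes (item b) |
| Hypoglycemia, assisted | Not needed | Met | CGM | CGM only |
| Hyperglycemia without ketosis | Not met | Not met | CGM, post-dinner glucose | Yes, as mean glucose and time in range |
| Ketosis short of DKA | Not met | Not met | Ketone-meter data | No |
| Infusion-site reaction, not severe, no antibiotics | Not met | Not met | Measured at set failure; picture above 3 mm, call above 10 mm | No (erythema and induration analysed in Part 2 only) |
| Infusion-site reaction, severe or needing antibiotics | Not met if foreseen | Uncertain | As above | No |
| Allergic reaction | Not met | Not met | No dedicated measure; period questionnaire | No |

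Notes on the table:

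1. Ketosis is not named in the risk list. It is foreseen elsewhere: Chapter 3 makes ketones above 0.6 mmol/L a trigger for set replacement, and Chapter 5 makes repeated values above 1.0 mmol/L without a set change a ground for considering withdrawal.
2. The skin rule is uncertain for infusion sites because the sentence setting the severity threshold names no site, while the sentence before it speaks of sensor wear.
3. Unexpected is not defined for this purpose. The nearest definition, for unanticipated device events, turns on nature, severity or incidence, so an unusually bad site reaction might qualify. This is why the right description is no assured record, rather than certain exclusion.
4. If a non-serious event enters only when already related, the later related/unrelated judgement is redundant for it. That judgement also omits the insulin, the one factor that Part 1 randomises.

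How thin would Part 1 site data be? Section 1.2.1 cites premature set end in 10% of 210 Fiasp infusions and 4% of 98 aspart infusions, not significant. Assume that premature end approximates set failure, that all 20 subjects complete 14 days on each insulin, and that a set is worn for 2, 3 or 4 days.

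- Sets per insulin = 20 × 14 / wear = 140, 93 or 70.
- Measured sets on Fiasp = 10% = 14, 9 or 7.
- Measured sets on aspart = 4% = 6, 4 or 3.

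So roughly one Fiasp set in 10 and one aspart set in 25 would yield a site measurement. Because set failure occurs after randomisation and may itself differ by insulin, a comparison within failed sets is not a randomised one.

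**The case against.** The strongest reply is that the quoted sentence defines a reportable event, while a separate section governs recording. On that reading the protocol already collects non-serious events. This is a fair reading, and the itching example supports it. But the two sections are never explicitly distinguished, and the added rules in the Definition section themselves speak of what is recorded and when a form is completed. The ambiguity therefore stands.

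Second, a reader might infer that nothing enters the adverse-event data unless it is serious, or unexpected and related. The documents do not support that. Assisted hypoglycemia without hospitalization counts under its own rule, and so does skin irritation that is severe or needs antibiotics.

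Third, a reader might infer that the missing events go uncollected. That is also unsupported. CGM covers ordinary high and low glucose. Sites are measured and photographed, subjects are told to inspect them daily and to contact staff about any skin reaction, weekly uploads are reviewed for safety, and the questionnaire after each blinded period asks participants and providers about disadvantages of that insulin. This reply largely succeeds for glucose. For allergy, ketosis and sites it leaves data that are not dated, graded events and are not compared by insulin.

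Fourth, the cited 10% and 4% might be taken as a count of lost adverse events. They cannot be: a premature set end is set performance, not a medical occurrence, and the cited difference was not significant. The figures are used above only to show how few sites would be measured.

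Finally, this is an unpowered pilot with no comparative safety test planned. That is a reason to keep the Part 1 table descriptive, not to omit it.

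**Conclusion.** The point holds in a limited form. Chapter 4 contradicts itself on what is recorded, and under its narrower rule three kinds of foreseen event have no assured adverse-event record when non-serious: allergic reactions, ketosis short of DKA, and infusion-site reactions that are not severe. Severe or antibiotic-treated infusion-site reactions are uncertain. In Part 1, neither adverse events nor site findings enter the planned comparison, and site findings come only from failed sets.

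The consequence is a weak basis for comparing the tolerability of the two insulins. It is not an absence of safety data, and it does not affect the glycemic comparisons. The conclusion about the definition needs no numerical assumption. The estimate of 7–14 measured Fiasp sets and 3–6 aspart sets rests on full enrolment, on 2- to 4-day wear, and on treating premature end as failure. The change should be made, since it is cheap and serves the study's stated purpose.

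**What to change.** In Chapter 4, separate recording from reporting:

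- Record every untoward medical event, whether or not it is expected or related, from the start of blinded insulin in Part 1 and from enrolment for subjects who join only Part 2. Capture onset date, insulin period, intensity, and relatedness to insulin, device or procedures.
- Leave non-severe high and low glucose to the CGM outcomes, so that forms are not filled with ordinary glucose excursions. The existing rules for assisted hypoglycemia and DKA stay as they are.
- Keep the present definition as the rule for prompt reporting.
- State that the skin-irritation rule covers infusion sites as well as sensor sites.

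In Chapter 6, add a descriptive Part 1 table by insulin period of adverse events and of the infusion-site findings already collected. A footnote should say that site findings come only from failed sets, and the number of failed sets per insulin should be shown as the denominator. The table does not remove that selection. Recording at every set change, as Part 2 already asks, would do so, but that is a separate decision about data collection.

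The cost is a wording change and modest extra data entry for up to 20 subjects per part. Treatment and visits are unchanged.
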